7.4.2 Reporting of Serious Adverse Events

The Sponsor will collect SAEs from the time of signing of the ICF until Day 60 days (± 3 days) or until the date of death, whichever occurs first. Nonetheless, the Sponsor will evaluate any safety information that is spontaneously reported by an Investigator beyond the time frame specified in the protocol.

All SAEs (as defined above) that occur after first study treatment administration regardless of relationship to the study drug(s)/IMP(s) must be reported immediately, and always within 24 hours to the Pharma Mar S.A. Pharmacovigilance Department, electronically by completing the applicable e-CRF section. Only in situations of electronic system failure or pregnancy exposure during the clinical trial, can SAEs be reported using paper on a “SAE form” by fax [REDACTED], e-mail [REDACTED] or Pharmacovigilance Department telephone [REDACTED]

████████ for out of office hours (Greenwich Meridian Time [GMT]) assistance on SAE reporting. In case of electronic system failure or pregnancy exposure during the clinical trial, SAEs initially reported by alternative methods (not electronically), must be followed by a completed electronic SAE reporting on e-CRF from the investigational staff within one working day.

SAEs occurring during the screening phase (from ICF signature to randomisation) and after off-study will be reported using a paper "SAE form" that must be forwarded as mentioned above always within 24 hours to the Pharma Mar S.A. Pharmacovigilance Department by fax or email.

All SAEs, Treatment-related adverse events, and treatment-emergent adverse events of special interest must be followed until the event or its sequelae resolves or stabilizes to at least grade 1, or to an acceptable level according to the Investigator and the Sponsor or his/her designated representative.

7.4.3 Reporting Pregnancy Cases Occurred within the Clinical Trial

National regulations require that clinical trial Sponsors collect information on pregnancies occurring during clinical trials, in which exposure to the IMP(s) at any time during pregnancy, via either maternal or paternal exposure, is suspected.

Therefore, pregnancy and suspected pregnancy (including a positive pregnancy test regardless of age or disease state) of a female patient occurring within six months from the patient's last plitidepsin administration, or of the female partner of a male patient occurring while the patient is on study drugs or within six months after the last plitidepsin administration, are considered immediately reportable events.

The Investigator will report the following events immediately and always within 24 hours from first knowledge:

- Any occurrence of a pregnancy where any kind of exposure to the IMP(s) is suspected.
- Possible exposure of a pregnant woman.
- All reports of elevated/questionable or indeterminate beta human chorionic gonadotropins (β -hCGs).

Immediately after detecting a case of suspected pregnancy in a female patient, the decision on her continued participation in the clinical trial will be jointly taken by the patient, the Investigator and the Sponsor, with the patient's best interest in mind. A decision to continue the pregnancy will require immediate withdrawal from the trial.

Any pregnancy, suspected pregnancy, or positive pregnancy test must be reported to Pharma Mar S.A. Pharmacovigilance immediately using the Pregnancy Report form.

The Investigator will follow the pregnancy until completion/termination and must notify the outcome of the pregnancy to the Pharmacovigilance Department at PharmaMar within 24 hours of first knowledge as a follow-up to the initial Pregnancy report.

For any event during the pregnancy which meets a seriousness criterion (including fetal or neonatal death or congenital anomaly) the Investigator will also follow the procedures for reporting SAEs (complete and send the SAE form to Pharma Mar S.A. Pharmacovigilance within 24 hours of the Investigator's knowledge of the event).

All neonatal deaths that occur within 30 days of birth should be reported, without regard to causality, as SAEs. In addition, any infant death at any time thereafter that the Investigator suspects is related to the exposure to the study drug(s)/IMP(s) should also be reported to Pharma Mar S.A. Pharmacovigilance within 24 hours of the Investigators' knowledge of the event.

7.5 ADVERSE EVENTS MONITORING

Safety review will be performed at Pharma Mar, S.A. once the SAE forms have been received and the e-CRFs have been completed by the Investigator.

Periodic safety review of clinical data will be performed; an IDMC will be established to provide study oversight. The IDMC will be established and operated in compliance with the FDA Guidance for Industry "Establishment and Operation of Clinical Trial Data Monitoring Committees". The description of the process will be outlined in the IDMC Charter.

SAEs will be collected, assessed and reported as per the applicable Regulations by the Pharmacovigilance Department.

Non-serious AEs will be checked for accuracy against the e-CRF during monitoring visits by the monitor.

7.6 PHARMACOKINETICS

7.6.1 Blood Sampling

Blood samples will be collected from the first 30 patients enrolled in this study (experimental arms), at the time points depicted in [Table 3](#). In the event that any of the first 30 patients does not complete all three doses, the first 30 patients who complete all 3 doses will be included.

Table 3 Samples for pharmacokinetic evaluations.

Study Day	Sample number	Time point (absolute time from the start of first plitidepsin infusion)	Collection window
1	1	0 h	Before first infusion
3	2	48 h	Before SOI (-20 to -1 m)
	3	49 h	5 m before EOI (± 4 m)
	4	52 h	3 h after EOI (± 30 m)
	5	55 h	6 h after EOI (± 1 h)
4	6	72 h	23 h after EOI (± 4 h)
8	7	168 h	119 h after EOI (± 24 h)

Abbreviations: EOI=end of third infusion; h, hour; min, minute; SOI=start of third infusion

The infusion rate will be predetermined to ensure that the doses of plitidepsin are infused in 60 min, at a constant rate. In order to obtain reliable PK information, the infusion rate should not be modified once the infusion begins. If a variation in the infusion time eventually occurs, it is very important this to be reflected in the e-CRF. The accurate recording of actual dosing and sampling times is much more important than the strict adherence to the scheduled times.

Blood samples will be obtained into a vacutainer tube by using a peripheral catheter placed in a vein of the arm opposite to the side used for drug infusion. Even the last sample must never be collected from the catheter used for drug infusion.

A Laboratory Manual will be provided with details on collection and storage of PK samples. Please read it carefully before PK sampling. The blood-containing tubes will be stored frozen until their shipment to the Central Laboratory for PK Samples (see details in the Study Contacts). All the material for PK procedures will be provided by the Sponsor).

7.6.2 Analytical Procedures

Blood samples will be analysed to determine concentrations using validated, specific, and sensitive liquid chromatography/mass spectrometry/mass spectrometry (LC-MS/MS) methods by or under the supervision of the Sponsor.

7.6.3 Pharmacokinetic Parameters

Pharmacokinetic analysis will be the responsibility of the Sponsor in accordance with the current Clinical Pharmacokinetics guidelines on population pharmacokinetic analyses (88, 89). Clearance and volume of distribution will be the primary parameters of interest for the population PK analysis. Additional PK parameters will be calculated, if deemed appropriate.

8. STATISTICAL METHODS

This is an exploratory basket study to adequately approach the heterogeneity of clinical conditions included under the concept of immune compromise.

The study implements a Bayesian methodology. This decision has been adopted after taking into account the relative low frequency of the conditions under study, the relative absence of prospective data of the outcomes of COVID-19 for the study populations (most of the available data are retrospective and belong to the early waves of the pandemic, with different viral variants than nowadays), along with the changing medical practices in these settings. Under these premises, a Bayesian approach is more appropriate in terms of efficient decision-making process, and will provide novel information for future therapeutic development in these clinical conditions (90).

The trial will use a minimally-informative prior of $N(0,1)$ to update the information provided by the trial data to produce a posterior distribution.

The resultant posterior distribution will serve as a starting point for further trials within this area, whether as a key part of any information data packs provided to experts ahead of an elicitation meeting, or directly as the informed prior or hypotheses for further trials (91) (92).

A calibrated Bayesian hierarchical model (CBHM) described by Chu and Yuan (93) will be used to analyse the data, allowing data to be analysed by group and results from each group will be used to enrich the data of the other groups. The calibration of the model allows strong information sharing when the treatment effect is similar among baskets, and shrinks that sharing towards 0 as the treatment effect becomes more heterogeneous.

An overall type I error of 5% was used in analysing by means of credible regions the OR against a null of OR=1 [$\log(\text{OR})=0$], the case where no discernible difference is induced from intervention.

Simulation was used to perform sensitivity analysis on a range of informed priors against a minimally-informative prior to ensure that its use would not impact the results on the data too far.

The statistical methods for this study are described in a detailed statistical analysis plan (SAP).

8.1 SAMPLE SIZE CALCULATION

Our intention is to conduct this study with 4 groups of immunocompromised patients.

A) Randomised groups (1-3)

Patients in three of the four groups will be randomly assigned to one of two arms. Each randomised group will have a sample size of 40 patients (20 in the experimental arm, 20 in the control arm).

Given the exploratory nature of this phase II study, this sample size has been chosen based on operational considerations to allow the feasibility of accrual in this relatively small population and also provide preliminary estimates to establish an updated prior distribution of the mortality rates for further investigation using Bayesian methods in a potential Phase III study.

The operating characteristics of the calibrated Bayesian hierarchical model (CBHM) described by Chu and Yuan (93) have been investigated by means of the CBHM package from Yuan at MD Anderson Cancer Center (94), and with reference to the JAGS program running in R version 4.2.1 (95) on Microsoft Windows 10.

Within the CBHM simulations, 5000 Markov-chain Monte Carlo (MCMC) repetitions per scenario were simulated with a range of operating characteristics for the null, alternative and true mortality rates moving from 5% to 95% in steps of 5% ([Table 4](#)). A maximum sample size of 40 per randomised group was set through the CBHM simulations, which in turn determines whether there is a need for the total sample size to be allocated. Within all simulations, the full 120 patients were used, suggesting that this is the minimum sample size that enables decision-making. As an example, if the mortality rate in each group is 20% and we target a clinically meaningful reduction of 12.5% in the experimental arm ($H_0=20\%$, $H_1=7.5\%$), and the assumed true mortality rate is 7.5%, the simulation demonstrates that a sample size of 40 per basket will allow for a posterior probability around 0.9 in each basket (i.e. 90% probability that the

experimental arm is better than the control in each basket), ranging from 0.87 (when the data from the fastest basket is analysed) to 0.915 (at the end of the accrual of the last basket) (type I error rate= 0.05).

Table 4 Example of simulated posterior probabilities for sample size definition.

Mortality rate – control arm (null)	Mortality rate – experimental arm (alternative)	True mortality rate	Sample size per basket	Posterior probability 1st basket	Posterior probability 2nd basket	Posterior probability 3rd basket
20%	7.5%	7.5%	30	0.82	0.84	0.865
20%	7.5%	7.5%	40	0.87	0.88	0.915
20%	7.5%	7.5%	50	0.895	0.905	0.93
20%	7.5%	7.5%	60	0.905	0.925	0.97
20%	7.5%	7.5%	70	0.945	0.98	0.985
20%	7.5%	7.5%	80	0.96	0.985	0.985

The full output of the simulations performed can be found in the Statistical Analysis Plan.

B) Non-controlled group 4*

Many different clinical conditions cannot be classified into one of the 3 randomised groups and have been pooled into a fourth group of 30 patients. As there is a remarkable intragroup heterogeneity, this group will not be controlled and will contribute to the objective of increasing safety knowledge of plitidepsin. A Fleming's phase II procedure with a 1-stage design has been used to estimate the sample size needed to rule out that plitidepsin induces drug-related SAEs in at least 35% of the patients (null hypothesis), and to confirm that the respective rate is 10 % or lower (alternative hypothesis), with a type I error of 0.05 and a power of 90%.

If at least 25 patients out of a total sample of 30 do not experience a drug-related SAE, the null hypothesis will be rejected.

*Not applicable in Spain

8.2 ANALYSIS POPULATIONS

8.2.1 Full Analysis Set (FAS) Population

All randomised patients who have taken at least 1 dose of study treatment (plitidepsin or control) and have completed follow-up for survival until day 30 (± 2). Patients who die before the end of follow-up period will also be included in the FAS population. FAS population will be analysed according to their randomised treatment arm.

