5.2.2 Treatment Discontinuation

Treatment discontinuation occurs when an enrolled patient ceases to receive the study treatment regardless of the circumstances.

The primary reason for any treatment discontinuation will be recorded on the patient's electronic Case Report Form (e-CRF).

A subject may stop the study treatment but desirably should continue to the end of study. Should a patient decide to prematurely discontinue the study treatment (refuses treatment), all efforts will be made to complete and report the observations as thoroughly as possible. He/she should be asked if he/she can still be contacted for further information. The outcome of that discussion should be documented in the medical records. Whenever possible, patients who receive at least 1 dose of plitidepsin and withdraw from the study will be followed for at least 31 days (± 3 days) after administration of the last dose of plitidepsin to follow-up on possible open TEAEs at withdrawal or for potential late-onset treatment-related TEAEs.

Patients will receive the study treatment(s) while it is considered to be in their best interest. Specifically, individual treatment of a given patient will be prematurely ended if:

- Unacceptable toxicity despite allowed/applicable medical prophylaxis or therapy.
- Intercurrent illness of sufficient magnitude to preclude safe continuation of the study treatment.
- Patient's refusal (follow-up has to be continued for those patients who refuse treatment, but do not withdraw consent) and/or non-compliance with study requirements.
- A major protocol deviation that may affect the risk/benefit ratio for the participating patient.
- Investigator's decision.

A rapid disease progression per se is not an indication for treatment discontinuation and needs additional clinical input. Patients who are withdrawn for any reason must not be re-treated in the context of this study at any time.

All cases of treatment discontinuation must be documented (date and reason) in the eCRF. Patients will be informed that they have the right to withdraw from the study at any time, without prejudice to their medical care, and are not obliged to state their reasons.

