8.5 SUMMARY OF ESTIMANDS AND STATISTICAL TESTS

The primary estimand corresponding to the primary endpoint is defined as:

Treatment: Participants will be randomised to receive plitidepsin versus control in each group.

Population: Participants as defined through the inclusion and exclusion criteria, who have been randomised to the trial and who have taken at least 1 dose of study treatment (plitidepsin or control).

Variable:

–1-month all-cause mortality rate (Day 30 since randomisation).

Intercurrent events:

–The participant's data are collected and included in the analysis without regard for treatment discontinuation (treatment-policy strategy).

–In the event of the participant initiating another non-protocol therapy, 1-month all-cause mortality rate will be evaluated regardless of initiation of new non-protocol therapy (treatment-policy strategy).

Population level summary: the posterior probability associated for the odds ratio of 1-month all-cause mortality rate from a Bayesian logistic regression for each group comparison.

Below a summary table where main/supportive analyses are described. P values except for the primary analysis have to be considered as exploratory and nominal values will be shown.

Endpoints	Analyses
Efficacy primary endpoint	
1-month all-cause mortality rate.	
 -Bayesian odds ratio (primary analysis by CHBM) -Bayesian odds ratio (Berry's Method) - Unstratified odds ratio (Univariate Logistic regression) - Stratified odds ratio (Multivariate Logistic regression)
Key secondary endpoint	
Time to confirmed negativisation in SARS-CoV-2 antigen test or RT-PCR Ct > 30.	
 -Kaplan-Meier (unstratified and stratified) -Cox regression (unstratified and stratified)
Efficacy secondary endpoints	
Time to sustained end of COVID-related hospital care from the time of randomisation. Sustained discharge is defined as no subsequent admission within 30 days of initial end of hospital care [up to day 60 (± 3)], related to either COVID-19 or COVID-19 therapy	
 -Kaplan-Meier (unstratified) -Cox regression (unstratified)
Time to sustained improvement (defined in Section 7.1.3) and resolution of selected COVID signs/symptoms (See Appendix 10 - COVID-19 signs/symptoms checklist).	
 -Kaplan-Meier (unstratified) -Cox regression (unstratified)

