8.6.2.1 Full Analysis Set (FAS) Population

All randomised patients who have taken at least 1 dose of study treatment (plitidepsin or control) and have completed follow-up for survival until day 30 (± 2). Patients who die before the end of follow-up period will also be included in the FAS population. FAS population will be analysed according to their randomised treatment arm.

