8.6.2.2 As Treated Population

All patients who received any exposure to study treatment (plitidepsin or control). As Treated population will be analysed according to the treatment they actually received.

Day 1 therapy is defined as any exposure to study treatment (partial or complete).

<NOTE: Due to the premature study closure no PP specific outputs or sensitivity analyses will be generated in populations other than the FAS for baseline and efficacy analyses and safety population for safety analyses>.

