9.0 Conventions and Derivations

Variables reported with different units will be homogenized to standardized variables following the International System of Units (e.g. laboratory tests, biometrical assessments...) unless otherwise specified.

By default, all results will be rounded to one decimal place, except when variables are integer, which will be reported without decimals (e.g., age in years). Percentages for 0 counts will not be presented and 100% values will be presented with no decimal places. For representing p-values four decimals will be selected as default but they could be rounded to fewer decimals if necessary.

Missing values will not be included in the calculation of outputs. Unless otherwise noted, missing data will not be imputed or carried forward.

For patients who discontinue treatment due to adverse events (related or not to study treatment) every effort should be made to remain under study follow-up, anyway, if information is lost before day 28 the conservative value of death will be also imputed.

Patients with no available data for any time-to event efficacy endpoint will be censored at time 0. EOS: Day 60 (± 3) or date of early study termination, if applicable. Patients not yet achieving the time to event endpoint will be censored at the last valid assessment prior to EOS. Efron's method will be used to handle ties.

Assessment windows as specified in the clinical protocol will be respected, see protocol Appendix 13 'Schedule of Assessments and Procedures' for definitions of trial days. Baseline is defined as latest test performed between screening and drug administration.

Change from baseline (%) is defined as: $(\text{test value} - \text{baseline value}) / \text{baseline value} \times 100$.

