11.6.1 Primary Estimand

The primary estimand corresponding to the primary endpoint is defined as:

Treatment: Participants will be randomised to receive plitidepsin versus control in each group.

Population: Participants as defined through the inclusion and exclusion criteria, who have been randomised to the trial and who have taken at least 1 dose of study treatment (plitidepsin or control).

Variable:

–1-month all-cause mortality rate (Day 30 since randomisation).

Intercurrent events:

- The participant's data are collected and included in the analysis without regard for treatment discontinuation (treatment-policy strategy).
- In the event of the participant initiating another non-protocol therapy, 1-month all-cause mortality rate will be evaluated regardless of initiation of new non-protocol therapy (treatment-policy strategy).

Population level summary: the posterior probability associated for the odds ratio of 1-month all-cause mortality rate from a Bayesian logistic regression for each group comparison including point estimate and credible interval will be shown.

The cut-off for considering further clinical development of plitidepsin in each randomized group will be a posterior probability of superiority for the experimental arm equal to or greater than 65%.

<NOTE: Due to the premature study closure no Bayesian specific outputs will be generated and descriptive data will be shown>.

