Adverse events of special interest (AESIs).	-Frequencies (severity grade by NCI-CTCAE v5)	-As treated population
Serious adverse events (SAEs).	-Frequencies (severity grade by NCI-CTCAE v5)	-As treated population
Drug related Serious Adverse Events (i.e., SARs).	-Frequencies (severity grade by NCI-CTCAE v5)	-As treated population
Adverse events leading to treatment discontinuation.	-Frequencies (severity grade by NCI-CTCAE v5)	-As treated population
Deaths (COVID-19-related/all).	-Frequencies	-As treated population
Change respect to baseline in individual study-defined laboratory parameters (See Protocol Section 5.7, 5.8 and 5.9 and Appendix 8 - Clinical Laboratory Analyses).	-Frequencies (severity grade by NCI-CTCAE v5)	-As treated population
Change respect to baseline in individual vital signs (See Protocol Section 5.7, 5.8 and 5.9).	-Frequencies	-As treated population
Other Secondary/Exploratory Endpoints		
Percentage of patients requiring advanced oxygen support on Days 4 (± 1), 8 (± 1), 15 (± 1), 30 (± 2), and 60 (± 3).	-Frequencies	-FAS population
Time to intensification of respiratory support (WHO >5) (See Protocol Appendix 1 – 11-Point World Health Organization (WHO) Clinical Progression Scale).	-Kaplan-Meier (unstratified)	-FAS population
Total duration of advanced oxygen support.	-Summary statistics	-FAS population

Endpoints	Analyses	Population
Percentage of patients requiring high-flow oxygen on Days 4 (± 1), 8 (± 1), 15 (± 1), 30 (± 2), and 60 (± 3).	-Frequencies	-FAS population
Total duration of high-flow oxygen therapy per patient.	-Summary statistics	-FAS population
Percentage of patients requiring non-invasive mechanical ventilation on Days 4 (± 1), 8 (± 1), 15 (± 1), 30 (± 2), and 60 (± 3).	-Frequencies	-FAS population
Total duration of non-invasive mechanical ventilation per patient.	-Summary statistics	-FAS population
Percentage of patients requiring invasive mechanical ventilation or ECMO on Days 4 (± 1), 8 (± 1), 15 (± 1), 30 (± 2), and 60 (± 3).	-Frequencies	-FAS population
Total duration of invasive mechanical ventilation or ECMO per patient.	-Summary statistics	-FAS population
Percentage of patients requiring admission to ICU on Days 4 (± 1), 8 (± 1), 15 (± 1), 30 (± 2), and 60 (± 3).	-Frequencies	-FAS population
Total duration of intensive care unit (ICU) stay.	-Summary statistics	-FAS population
Time to onset of additional (i.e., not present at baseline) immune-modulating drugs.	-Kaplan-Meier (unstratified)	-FAS population

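### The full analysis set drops dosed patients lost alive before Day 28, so it does not match the primary estimand, and the death imputation names only AE discontinuers whom that set excludes as written

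*Protocol*

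**What the plan says.** Protocol 8.2.1 defines the FAS as "All randomised patients who have taken at least 1 dose of study treatment (plitidepsin or control) and have completed follow-up for survival" to Day 30 (±2). SAP 8.6.2.1 repeats this and both documents make one exception: "Patients who die before the end of follow-up period will also be included in the FAS population".

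The primary estimand (Protocol 8.5, SAP 11.6.1) takes eligible participants "who have been randomised to the trial and who have taken at least 1 dose of study treatment". It sets no follow-up condition and applies a treatment-policy strategy to treatment discontinuation and to new non-protocol therapy.

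SAP 9.0 leaves missing data unimputed by default. It makes an exception for patients who stop treatment because of adverse events: "if information is lost before day 28 the conservative value of death will be also imputed".

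SAP version 3.0, written after early closure, reports the primary endpoint as frequencies in the FAS (Table 3, section 11.8). SAP 8.6.2 still mentions analyses in other populations, but the note under 8.6.2.2 withdraws them: "no PP specific outputs or sensitivity analyses will be generated in populations other than the FAS for baseline and efficacy analyses".

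**The concern.** Membership of the primary analysis set depends on what happens after randomisation. A patient who dies on Day 20 is counted. A patient last seen alive on Day 20 is not, although both belong to the estimand population. The FAS rate is therefore a complete-case rate, and the plan does not state the assumption under which it would estimate the stated target.

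The imputation rule does not close the gap. The patients it names have neither completed follow-up nor a recorded death, so the FAS as written has already removed them. If an imputed death is taken to satisfy the exception for patients who die, losses after an AE discontinuation become deaths while every other loss disappears. No sentence says which is meant, so two programmers could produce different primary tables.

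At stake is the between-arm contrast in the primary endpoint. It is descriptive under SAP version 3.0, but SAP 6.0 says the tables will allow a numerical comparison of the arms.

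**Working it through.** The plan states no loss rate and no figure for this point, so there is nothing to reproduce. The text is compared first; the numbers that follow are illustrations.

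**Populations side by side**

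| Condition | FAS | Primary estimand |
|---|---|---|
| Randomised | required | required |
| At least one dose | required | required |
| Followed for survival to Day 30 (±2), or dead | required | not required |

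The lower edge of the window is 30 − 2 = Day 28, the same day SAP 9.0 uses. The patients in dispute are those dosed and lost alive before Day 28.

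**One arm.** Assume the planned 20 patients per arm, all dosed, with 3 deaths and 2 lost.

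- (a) Literal FAS, both losses dropped: 3/18 = 16.7%.
- (b) Imputed deaths admitted, one loss an AE discontinuer and the other dropped: 4/19 = 21.1%.
- (c) Imputed deaths admitted, both losses AE discontinuers: 5/20 = 25.0%.
- Bounds over all dosed: 3/20 = 15.0% (both alive) to 5/20 = 25.0% (both dead).
- Kaplan-Meier, with losses placed on Days 4 and 10 and deaths on Days 8, 15 and 21: 1 − (18/19)(16/17)(15/16) = 16.4%.

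Against Kaplan-Meier, keeping deaths while dropping losses adds 0.3 points. The rest of the spread is unknown outcome.

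**Plitidepsin minus control, in percentage points.** Assume 20 dosed per arm and 4 control deaths. In the first three rows plitidepsin has 3 deaths; in the last it has 2. In the equal-loss row both arms have the same mix of AE and other losses.

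| Losses | (a) | (b) | (c) |
|---|---|---|---|
| 2 in each arm | 3/18 − 4/18 = −5.6 | 4/19 − 5/19 = −5.3 | 5/20 − 6/20 = −5.0 |
| 2 on control only | 3/20 − 4/18 = −7.2 | 3/20 − 5/19 = −11.3 | 3/20 − 6/20 = −15.0 |
| 2 on plitidepsin only | 3/18 − 4/20 = −3.3 | 4/19 − 4/20 = +1.1 | 5/20 − 4/20 = +5.0 |
| 2 on plitidepsin only, 2 deaths there | 2/18 − 4/20 = −8.9 | 3/19 − 4/20 = −4.2 | 4/20 − 4/20 = 0.0 |

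If the lost patients are all alive, the difference in the second and third rows is 3/20 − 4/20 = −5.0. The bounds are therefore −5.0 to −15.0 for control-only losses and −5.0 to +5.0 for plitidepsin-only losses. With equal losses the three results agree within 0.6 points; with no losses they coincide. Imputing death is not always conservative: on control it enlarges the apparent benefit.

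**Could losses differ by arm?** Protocol 5.2.2 says: "Whenever possible, patients who receive at least 1 dose of plitidepsin and withdraw from the study will be followed for at least 31 days" (±3) after the last dose. A last dose on Day 1 gives Day 1 + 31 ± 3 = Day 29–35; a last dose on Day 3 gives Day 31–37. Both lie past Day 28. No matching sentence covers withdrawing controls.

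**Smaller arms.** Accrual was to continue until the FAS target was reached (Protocol 5.4, SAP 8.6.1). Early closure ended that, so losses are not refilled. With 10 dosed, 2 deaths and 1 lost, the FAS gives 2/9 = 22.2%, with bounds of 2/10 = 20.0% to 3/10 = 30.0%.

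**The case against.** The strongest reply is that the FAS condition itself costs little. It moves the rate by 0.3 points against Kaplan-Meier; the wide bounds come from missing outcomes, which any analysis set would face. That stands, and it is why the bounds and loss counts carry most of the information in the remedy.

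Second, the treatment-policy strategy is not breached. It covers treatment discontinuation and new therapy, and a patient who stops treatment but is followed to Day 30 stays in the FAS. Loss to follow-up is missing data, and a complete-case rate can estimate the estimand under a suitable assumption. That is fair, but the plan states no such assumption, and its one imputation rule follows a different logic.

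Third, the case for unequal losses is limited. Continued follow-up after refusing treatment (Protocol 5.2.2) and the contact attempts in 5.2.4 apply to both arms. The 31-day sentence, if it matters, points to more losses on control, where the sign does not change in these examples. The sign change needs all losses on plitidepsin and a one-death gap. The −15.0 figure needs both lost controls to have stopped treatment for an adverse event, though a control may receive no antiviral at all. These points limit the size of the problem; they do not remove the conflict in the text.

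Fourth, SAP 11.1 already displays study withdrawals and SAP 11.0 provides listings, so losses could partly be reconstructed. Table 3 also tabulates deaths in the As Treated set. Neither output gives a Day-30 rate by randomised arm in the estimand population.

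**Conclusion.** The concern holds. The FAS adds a post-randomisation condition that the primary estimand lacks. The SAP 9.0 imputation either has no effect on the primary endpoint or treats AE losses as deaths and ignores the others. SAP version 3.0 plans no other efficacy population for the primary rate.

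The size depends on the number of losses and their split by arm, which the documents do not give. Two losses among 20 dosed put one arm between 15.0% and 25.0%. The readings of the between-arm difference separate materially only when losses are unequal. All these figures rest on assumed counts and on the planned arm size, which low recruitment may not have reached.

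The consequence is confined to a descriptive comparison, since the Bayesian analysis is no longer run. It remains the primary endpoint, and the rule should be corrected. A related gap is that *dose* is undefined for a control receiving best standard care alone, although Protocol 5.1 gives such a patient a treatment period ending on Day 4.

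**What to change.** - Delete the completed-follow-up condition. Define the FAS as all randomised patients in Groups 1–3 who started their assigned treatment, counting Day-1 best standard care as control treatment, analysed as randomised.
- Replace the AE-only imputation with one rule for unknown Day-30 status, applied identically in both arms whatever the reason for loss. Kaplan-Meier with censoring at the date last known alive would serve, with the non-informative-censoring assumption stated.
- Report the number lost per arm and how vital status after withdrawal was obtained in each arm.
- Show best-case and worst-case bounds for each arm and for the difference.
- Label the change as made after the unmasking decision of 19 March 2024 (SAP 8.2), and show the result under the current FAS beside it.
- Treat an all-randomised set as optional, and only where vital status is already held, because Protocol 5.7 limits the data collected on never-treated patients.

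The cost is SAP wording and one extra table. The estimand population does not change, and no extra patients or new data are needed. The drawback is a post hoc change to the primary set, which is why the current FAS result must stay visible.
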